I agree to ensure that the confidential information contained in this document will not be used for any purpose other than the evaluation or conduct of the clinical investigation without the prior written consent of Amgen Inc.

Signature

Name of Principal Investigator

Date (DD Month YYYY)

Approved

Protocol Synopsis

Title: A Phase 1b/2 Open Label, Dose Escalation Study of AMG 655 in Combination With AMG 479 in Subjects With Advanced, Refractory Solid Tumors

Study Phase: 1b/2

Indications

Part 1: Advanced, treatment-refractory solid tumors

Part 2: Advanced non-small cell lung cancer (NSCLC), colorectal cancer (CRC), pancreatic cancer, ovarian cancer, or sarcoma

Primary Objectives (Section 1.1)

Part 1: To identify a dose of AMG 655 in combination with AMG 479 that is safe and tolerated as determined by the incidence of dose limiting toxicity (DLT).

Part 2: To estimate the efficacy, as measured by the objective response rate (ORR; confirmed complete response [CR] and partial response [PR] using modified Response Evaluation Criteria in Solid Tumors [RECIST]) of AMG 655 in combination with AMG 479.

Secondary Objectives (Section 1.2)

Part 1

- To evaluate the safety and tolerability of AMG 655 in combination with AMG 479
- To evaluate anti-AMG 655 antibody formation and anti-AMG 479 antibody formation
- To evaluate the pharmacokinetics (PK) of AMG 655 and of AMG 479

Part 2

- To estimate the efficacy of AMG 655 in combination with AMG 479, as measured by time to response, duration of response, and progression-free survival (PFS)
- To evaluate the safety and tolerability of AMG 655 in combination with AMG 479
- To evaluate anti-AMG 655 antibody formation and anti-AMG 479 antibody formation
- To evaluate the PK of AMG 655 and of AMG 479

Exploratory Objectives (Section 1.3)

Parts 1 and 2

- To investigate the relationship between AMG 655 PK and AMG 479 PK and treatment outcomes (including clinical and pharmacodynamic endpoints)
- To investigate the baseline biomarker profile and pharmacodynamic response, as assessed by AMG 655 and AMG 479 biomarkers, and correlation with treatment outcomes
- Tumor tissue analysis of somatic gene mutations that function to regulate the IGF-1/IGF-1R and/or apoptosis pathways and other genes that are known to be involved in the development and progression of solid tumors (Required for subjects with CRC, ovarian cancer, and sarcoma; optional, if tissue is available, for subjects with NSCLC and pancreatic cancer).
- To investigate the genetic variations in cancer genes, drug target and pathway genes, and other biomarker genes, and correlation with treatment outcomes (optional for subjects; separate informed consent required).

Part 2

- To estimate the efficacy of AMG 655 in combination with AMG 479 using clinical benefit rate (CR, PR, and disease stabilization [SD] \geq 12 weeks, as measured by modified RECIST)

Approved

Study Hypotheses

Part 1: AMG 655 in combination with AMG 479 is safe and tolerated as determined by the incidence of DLT when administered to subjects with advanced, treatment-refractory solid tumors.

Part 2: The combination of AMG 655 with AMG 479 will have an acceptable safety profile and will be associated with at least 3 objective responses out of 15 evaluable subjects in at least 1 cohort (advanced NSCLC [squamous and/or non-squamous histology], CRC, pancreatic cancer, ovarian cancer, and/or sarcoma).

Study Design ([Section 3.1](#))

This is a multi-center, open-label, 2-part phase 1b/2 study of AMG 655 in combination with AMG 479.

Part 1 is a dose escalation segment to identify a dose of AMG 655 in combination with AMG 479 that is safe and tolerable as determined by the incidence of DLT. The maximum dose of AMG 655 planned is 15 mg/kg Q3W. There will be no intra-subject dose escalations in each of the planned dose cohorts.

Part 2 will open once a dose of AMG 655 has been identified that is safe and tolerated based on the incidence of DLT in Part 1 and evaluate the safety and estimate the efficacy (as measured by ORR) of AMG 655 at the dose selected in Part 1 in combination with AMG 479 for the treatment of patients with advanced NSCLC (Cohort 1: non-squamous histology; Cohort 2: squamous histology), CRC (Cohort 3), pancreatic cancer (Cohort 4), ovarian cancer (Cohort 5), and sarcoma (Cohort 6). Enrollment into the 6 cohorts will occur in parallel, independent of one another.

Parts 1 and 2

AMG 655 and AMG 479 treatment will be administered Q3W until disease progression, intolerable adverse event, death, withdrawal of consent, or administrative decision, for up to 24 months from the date of first study treatment (study day 1). Subjects who have completed 24 months of AMG 655 and/or AMG 479 treatment and who continue to benefit from treatment may be eligible for continued treatment with AMG 655 and/or AMG 479 by extension protocol or as provided for by the local country's regulatory mechanism ([Section 13](#)). Study treatment will cease if a subject experiences progressive disease (PD), death, intolerable adverse event(s), withdraws consent or due to an administrative decision (by the investigator or Amgen).

Radiological imaging (per modified RECIST) will be performed every 6 weeks (\pm 7 days) during the first 6 months of the study, and every 9 weeks (\pm 7 days) thereafter, until subjects develop PD (per modified RECIST) or begin a new cancer treatment. Safety follow-up visits will occur 30 ($+ 7$) days and 60 ($+ 14$) days after the last dose of protocol-specified treatment. Subjects will be contacted every 3 months (\pm 2 weeks) in the long-term follow-up, for up to 36 months from the date of the last subject enrolled, to assess survival.

To mitigate potential safety risks, the first 3 subjects in Part 1 will be enrolled at a rate of \leq 1 subject per week. The study team will review Part 1 dose level cohort data to make recommendations on dose escalation, dose selection and dose stopping. During Part 2 of the study, the study team will review safety data after a total of at least 15 subjects (Interim Analysis [IA] 1) and 45 subjects (IA 2) have been enrolled and have completed 1 cycle of treatment, and additionally as warranted during the conduct of this clinical trial.

The [Study Schema](#) is provided at the end of the Protocol Synopsis section.

Primary and Secondary Endpoints ([Section 10.2](#))

Part 1: The incidence of adverse events and clinical laboratory abnormalities defined as DLT

Part 2: ORR (confirmed CR and PR, by modified RECIST)

Approved

Secondary Endpoints

Part 1

- The incidence of adverse events and laboratory abnormalities not defined as DLT
- The incidence of anti-AMG 655 antibody formation and anti-AMG 479 antibody formation
- PK (C_{max} and C_{min} for AMG 655 and AMG 479)

Part 2

- Time to response
- Duration of response
- PFS
- The incidence of adverse events and laboratory abnormalities
- The incidence of anti-AMG 655 antibody formation and anti-AMG 479 antibody formation
- PK (C_{max} and C_{min} for AMG 655 and AMG 479)

Sample Size: Approximately 99 to 108 (Part 1: approximately 9 to 18 DLT-evaluable subjects; Part 2: approximately 90 response-evaluable subjects) (See [Section 3.3](#) and [Section 10.3](#))

Summary of Subject Eligibility Criteria: (See [Section 4.1](#) and [Section 4.2](#) for a complete list of eligibility criteria.)

Key Inclusion Criteria

- Locally advanced or metastatic, treatment-refractory solid tumors (Part 1)
- Locally advanced or metastatic NSCLC (up to 2 prior treatment regimens), CRC (up to 2 prior treatment regimens), pancreatic cancer (up to 1 prior treatment regimen), ovarian cancer (up to 2 prior treatment regimens), or sarcoma (up to 2 prior treatment regimens) (Part 2)
- Measurable disease (at least one measurable lesion) (Part 2)
- ≥ 16 years old
- Life expectancy ≥ 3 months
- Eastern Cooperative Oncology Group (ECOG) performance status 0 or 1
- Adequate organ function (liver, kidneys, bone marrow, coagulation, heart, glycemic function)

Key Exclusion Criteria

- Presence of uncontrolled central nervous system (CNS) metastasis
- Prior treatment with death receptor agonists (eg, rhApo2L/TRAIL [AMG 951], apomab, mapatumumab, lexatumumab, CS-1008)
- Prior treatment with IGF receptor antagonists (eg, CP-751,871, MK0646, AVE1642 or IMC-A12)
- Systemic chemotherapy, hormonal therapy, immunotherapy, experimental or approved anticancer proteins/antibodies therapy ≤ 28 days before enrollment, except:
 - In Part 1, patients may continue approved hormonal therapy as medically indicated
- Any prior or synchronous malignancy (except for non-melanoma skin cancer or in situ cervical cancer) other than the study disease, unless treated with curative intent with no evidence of disease ≥ 3 years before enrollment (Part 2)
- Any clinically significant medical condition other than cancer, including cardiovascular disease or chronic obstructive pulmonary disease, which in the opinion of the investigator could interfere with the safe delivery of study treatment or increase risk of toxicity

Approved

Investigational Product Dosage and Administration: See [Section 6, Treatment Procedures](#); [Section 11, Investigational Products](#); [Appendix C](#) for AMG 655 and AMG 479 Pharmacy Guides.

Part 1

Cohort 1: AMG 479 18 mg/kg plus AMG 655 1 mg/kg IV on day 1 of each Q3W cycle

Cohort 2: AMG 479 18 mg/kg plus AMG 655 3 mg/kg IV on day 1 of each Q3W cycle

Cohort 3: AMG 479 18 mg/kg plus AMG 655 15 mg/kg IV on day 1 of each Q3W cycle

There will be no intra-subject dose escalations in each of the planned dose cohorts. Alternative AMG 655 doses (eg, 0.3 mg/kg IV) and/or AMG 479 doses may be explored based on safety and PK data.

Part 2: AMG 479 18 mg/kg plus AMG 655 at the dose selected in Part 1 (up to 15 mg/kg) IV on day 1 of each Q3W cycle

AMG 655 and AMG 479 will be administered through a peripheral line or indwelling catheter using a nonpyrogenic, low protein binding filter with a 0.2- or 0.22-micron pore size in-line filter infusion set-up.

Control Group: There is no control group.

Key Study Procedures: See [Section 7.1](#) and Schedule of Assessments ([Appendix A](#)) for details.

Screening Procedures

- Review of inclusion and exclusion criteria
- Medication and medical history, concomitant medications/treatment(s), adverse events
- Vital signs: resting pulse, respiration, blood pressure, and temperature
- Physical examination, including height and weight
- ECOG performance status assessment
- Laboratory tests; including hematology, chemistry, coagulation, urinalysis, pregnancy test
- Submission of formalin-fixed, paraffin-embedded tumor tissue (paraffin tumor block, or slides) and associated pathology reports (Required for subjects with CRC, ovarian cancer, and sarcoma; optional, if tumor tissue is available, for subjects with NSCLC and pancreatic cancer).
- 12-lead electrocardiogram (ECG)
- Radiological imaging to assess disease extent (CT scan or MRI of the brain, chest, abdomen, and all other sites of disease; within 28 days prior to enrollment)

Treatment and Follow-up Procedures

- Recording of adverse events and concomitant medications
- Vital signs: resting pulse, respiration, blood pressure, and temperature
- Physical examination, including weight, and ECOG performance status assessment
- Laboratory tests; including hematology, chemistry, pregnancy test
- Samples for biomarkers and anti-AMG 655 and anti-AMG 479 antibodies
- Samples for AMG 655 and AMG 479 PK
- ECG
- Radiological imaging to assess disease extent (CT scan or MRI [same modality throughout the study] of the chest, abdomen, and all other sites of disease [except: brain imaging only as clinically indicated] every 6 weeks [\pm 7 days] during the first 6 months of the study, and every 9 weeks [\pm 7 days] thereafter)

Approved

Statistical Considerations: See [Section 10](#) for details.

Analyses will be presented separately for Part 1 and Part 2 of the study.

Part 1: A sample size of approximately 3 to 6 DLT-evaluable subjects per cohort was selected to identify a dosing regimen of AMG 655 in combination with AMG 479 that is safe and tolerated based on the incidence of DLT. A listing and summary of the incidence of DLT will be presented for each cohort. All other safety data collected in Part 1 of the study will be summarized using appropriate descriptive statistics. The study team will review Part 1 dose level cohort data after at least 3 subjects have completed the DLT window to make recommendations on dose escalation, dose selection and dose stopping.

Part 2

Approximately 90 subjects (15 response-evaluable subjects per cohort [tumor type]) will be enrolled in Part 2. This part of the study will identify tumor types, in which further study of AMG 655 in combination with AMG 479 is warranted, using the following criterion: at least 3 out of 15 subjects have an objective response (an ORR of at least 20%). If 2 or less responders are observed in a given cohort, then all other parameters of clinical benefit (including clinical benefit rate and PFS, within others) and of patient safety will be evaluated to determine if further study is warranted of the AMG 655 and AMG 479 combination in that tumor type. The primary endpoint is ORR. The proportion of subjects with an objective response (confirmed CR or PR by modified RECIST) per local investigator assessment with corresponding 95% exact confidence intervals will be presented for each Part 2 cohort. All safety data collected in part 2 of the study will be summarized per cohort and in aggregate over all cohorts using appropriate descriptive statistics. During Part 2 of the study, the study team will review safety data after a total of at least 15 subjects (Interim Safety Analysis [IA] 1) and 45 subjects (IA 2) have been enrolled and have completed 1 cycle of treatment, and additionally as warranted during the conduct of this clinical trial. Unless safety concerns arise, enrollment will not be stopped during the Part 2 safety reviews.

The primary analysis of Part 2 will provide the proportion of subjects with an objective response and is planned to occur after all subjects have had the opportunity to complete 4 cycles of treatment. If the recruitment rate is not consistent across cohorts, a piecewise approach to the primary analysis may be taken with the analysis for the quickest recruiting cohorts occurring first.

The final analysis of this study will occur after all subjects have progressed, died, or terminated the study for other reasons.

Sponsor/Licensee: Amgen, Inc.

Approved

Study Design and Treatment Schema

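### Does a Part 2 hypothesis that any one of six cohorts can satisfy, with 3 responses in 15, set too low a bar for the study?

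*Combined protocol and SAP*

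**What the plan says.** Under Study Hypotheses in the Protocol Synopsis, Part 2 expects the combination's safety to be acceptable and, on the response side, asks for "at least 3 objective responses out of 15 evaluable subjects in at least 1 cohort". Safety is therefore part of the hypothesis, although the synopsis does not quantify it.

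Under Study Design there are six cohorts. NSCLC supplies two of them ("Cohort 1: non-squamous histology; Cohort 2: squamous histology"), followed by colorectal, pancreatic, ovarian and sarcoma. "Enrollment into the 6 cohorts will occur in parallel, independent of one another".

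Under Statistical Considerations, Part 2, the size is given as "Approximately 90 subjects (15 response-evaluable subjects per cohort [tumor type]) will be enrolled in Part 2". The purpose is put this way: "This part of the study will identify tumor types, in which further study of AMG 655 in combination with AMG 479 is warranted". The criterion is the same 3 of 15, with 20% in parentheses as the corresponding ORR. The sentence after it begins "If 2 or less responders are observed in a given cohort, then all other parameters of clinical benefit" and goes on to say that these parameters, together with safety, decide whether further study is warranted in that tumor type. ORR is to be presented for each cohort with an exact 95% confidence interval.

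The primary objective of Part 2 is to estimate efficacy as measured by ORR. The supplied text states no alpha, power, null ORR or multiplicity adjustment.

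**The concern.** Read as a success criterion for the study, the hypothesis is a union: one cohort out of six is enough, and each cohort brings its own chance of passing by luck. Nothing in the wording allows for six attempts. A combination with a modest and uniform ORR could then be reported as having met its hypothesis on the strength of its luckiest cohort.

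Two further features add to the unease. The plan glosses 3 of 15 as an ORR of at least 20%, which could be taken as a statement about the true rate. And a cohort whose true ORR is 20% would fall short of 3 of 15 about 40% of the time. If the hypothesis drove the decision to go on, a weak combination could advance on chance and a useful one could be dropped.

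**Working it through.** **Inputs from the synopsis.** Six cohorts; 15 response-evaluable subjects in each; bar of 3 or more responses; cohorts enrolled independently.

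**Input assumed.** A true ORR, p, equal in all six cohorts. The documents do not give one, so a range is shown.

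**The plan's own figures.** 6 × 15 = 90 subjects, and 3/15 = 20%. Both reproduce exactly.

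**One cohort.** With X the number of responders among 15, P(X ≥ 3) = 1 − P(0) − P(1) − P(2), where P(k) is the binomial probability of k responders.

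At p = 10%: P(0) = 0.9^15 = 0.2059; P(1) = 15 × 0.1 × 0.9^14 = 0.3432; P(2) = 105 × 0.1² × 0.9^13 = 0.2669. The sum is 0.8159 to four decimals when the unrounded terms are added, so P(X ≥ 3) = 0.1841.

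**At least one of six.** 1 − (1 − 0.1841)^6 = 1 − 0.8159^6 = 0.705. The expected number of cohorts reaching the bar is 6 × 0.1841 = 1.10.

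| True ORR in all cohorts | One given cohort reaches 3/15 | At least one of six does |
|---|---|---|
| 5% | 3.6% | 19.8% |
| 7.5% | 9.7% | 45.9% |
| 10% | 18.4% | 70.5% |
| 15% | 39.6% | 95.1% |
| 20% | 60.2% | 99.6% |

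If NSCLC were counted as a single cohort of 15, giving five cohorts, the 10% figure would be 1 − 0.8159^5 = 0.638.

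**What a bare pass shows.** The exact (Clopper-Pearson) 95% interval for 3/15 runs from 4.3% to 48.1%, so it excludes neither 5% nor 10%. This is the interval that the plan already undertakes to present for a cohort with that result.

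**A stricter study-level bar.** Requiring 4 of 15 in at least one cohort changes the figures as follows.

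| True ORR | One cohort, 3/15 | One cohort, 4/15 | Any of six, 4/15 |
|---|---|---|---|
| 5% | 3.6% | 0.6% | 3.2% |
| 10% | 18.4% | 5.6% | 29.0% |
| 15% | 39.6% | 17.7% | 69.0% |
| 20% | 60.2% | 35.2% | 92.6% |
| 30% | 87.3% | 70.3% | 99.9% |

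**Which column matters.** The only rule with a consequence in the supplied text is the one under Statistical Considerations, and it works by tumor type. Its operating characteristics are those of one cohort. The any-of-six column describes a sentence in the hypothesis to which no action is tied.

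**The case for a change.** The best argument for a change is that the sponsor wrote a hypothesis with a numerical pass mark, and readers of the results will ask whether it was met. At a true ORR of 10% everywhere, the highest of six cohorts is expected to show 3.06 responses out of 15, an observed rate of 20.4%. The pass mark is then roughly what the luckiest cohort would show at half the rate the plan names. Removing the any-cohort phrase would cost nothing, and it would bring the hypothesis into line with the estimation objective and the cohort-level rule.

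Much of this stands. As a claim about the whole study, the hypothesis is weak, and meeting it should not be presented as proof of activity. A cohort-by-cohort wording would be tidier.

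Three parts do not carry through to a required change. First, 70% is not a type I error. No null rate is named, no test is planned, and nothing in the supplied text says that 10% is uninteresting in these populations. The figure moves from 20% to 95% as the assumed rate goes from 5% to 15%.

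Second, the 40% chance of falling short at a true ORR of 20% is not a 40% chance of abandoning the tumor type. Two or fewer responders leads to a review of clinical benefit rate, PFS and safety, among other things. That flexibility also means 3 of 15 does not by itself cap false advancement, but this is a deliberate feature of an exploratory screen.

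Third, the 20% in parentheses directly follows the count of 3 in 15. A statistician will read it as the observed proportion, and the interval reported with it will show how little it pins down.

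**Conclusion.** The concern is arithmetically sound but does not call for a change. The any-cohort hypothesis would be met about 20%, 46%, 70% and 95% of the time at a common true ORR of 5%, 7.5%, 10% and 15%. This assumes independent cohorts of exactly 15 and leaves the safety component aside. The decision that Part 2 informs is taken per cohort, with corresponding chances of 3.6%, 9.7%, 18.4% and 39.6%. Leniency at that level is a fair trade-off in small single-arm screening cohorts that are reported by estimate and interval.

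None of the possible changes is needed. Restating the hypothesis by cohort and labelling 20% as observed would be optional tidying that alters no analysis or decision. Adding pass probabilities would be extra detail, and Section 10.3, which the synopsis cites but which was not available here, may already give them. A 4-of-15 study-level bar would set a second standard beside the screening rule. It would lower a cohort's chance of passing at a true ORR of 20% from 60% to 35%, and would still be met by at least one of six cohorts 69% of the time at 15%.

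### Does 36 months of survival follow-up with no overall survival endpoint in the synopsis leave data that the plan fails to use?

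*Combined protocol and SAP*

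**What the plan says.** Protocol Synopsis, Study Design (Parts 1 and 2), on long-term follow-up: "Subjects will be contacted every 3 months" (with a 2-week window), and this continues "in the long-term follow-up, for up to 36 months from the date of the last subject enrolled, to assess survival".

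The efficacy measures named for Part 2 are:
- Primary, under Statistical Considerations: "The primary endpoint is ORR".
- Secondary, under Secondary Objectives: "as measured by time to response, duration of response, and progression-free survival (PFS").
- Exploratory, under Exploratory Objectives: "To estimate the efficacy of AMG 655 in combination with AMG 479 using clinical benefit rate".

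Part 1 lists dose-limiting toxicity, other safety, antibody and PK endpoints only.

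Statistical Considerations, Part 2, describes two efficacy analyses. The primary analysis "is planned to occur after all subjects have had the opportunity to complete 4 cycles of treatment". For the last one: "The final analysis of this study will occur after all subjects have progressed, died, or terminated the study for other reasons".

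For a cohort with 2 or fewer responders, the same section turns to safety and to "all other parameters of clinical benefit (including clinical benefit rate and PFS, within others") when deciding whether further study is warranted.

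**The concern.** Survival is collected for a stated purpose, but the synopsis attaches no endpoint to it. PFS does not fill the gap, because deaths after progression do not enter PFS, and those are the deaths that long-term contact is set up to find. The final-analysis condition can be met by progression alone, so the last described analysis may take place while many subjects are still being followed.

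Two things would be at stake. Per-cohort survival could go unreported or be reported from an immature cut. And because the list of clinical-benefit parameters for low-response cohorts is open-ended, survival could be brought into that judgement, or left out of it, after the results are known.

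**Working it through.** **1. The plan's own figures.** Part 2: 6 cohorts × 15 = 90. Part 1: 3 × 3 = 9 to 3 × 6 = 18. Total: 99 to 108. Criterion: 3/15 = 20%. All reproduce, and none depends on survival. Follow-up of 36 months at 3-month intervals is about 12 contacts.

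**2. When the final-analysis condition could be met.** The documents give no PFS, accrual or survival assumption, so what follows is illustration. Assume 90 subjects, the last enrolled at time 0 and the other 89 uniformly over the previous 12 months, exponential progression with rate L = ln 2 / median, and no other way of meeting the condition. Then

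P(met before t) = (1 − e^(−Lt)) × [1 − e^(−Lt)(1 − e^(−12L))/(12L)]^89.

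For a 3-month median and t = 36: e^(−36L) = 2^(−12) = 0.000244, and (1 − 2^(−4))/(4 ln 2) = 0.9375/2.773 = 0.338. So P = 0.99976 × (1 − 0.0000825)^89 = 0.992.

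| Assumed PFS median (months) | Mean trigger (months after last enrolment) | P(before month 36) |
|---|---|---|
| 2 | 10.6 | 1.00 |
| 3 | 17.4 | 0.99 |
| 4 | 24.4 | 0.93 |
| 6 | 38.8 | 0.46 |

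Accrual over 24 months gives means of 8.8, 14.8, 21.2 and 34.8. Starting every clock at the last enrolment, which overstates the time, gives 14.7, 22.0, 29.3 and 44.0, with probabilities 1.00, 0.98, 0.84 and 0.24. A trigger before the end of follow-up is therefore plausible at short PFS medians.

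**3. Deaths left after the trigger.** Simulation under the 12-month accrual model, adding exponential survival after progression and no death before it. The entries are mean deaths among 90 subjects between the trigger and month 36.

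| PFS median (months) | Post-progression median 3 | 6 | 12 |
|---|---|---|---|
| 2 | 9 | 22 | 33 |
| 3 | 5 | 13 | 22 |
| 4 | 3 | 8 | 13 |
| 6 | 1 | 2 | 3 |

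With unequal cohort medians (2, 2, 3, 3, 4, 6) and a post-progression median of 6 months, the figure is about 7 of 90, or roughly one per cohort.

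**4. A rule that this model leaves out.** Under Study Design, imaging stops at progression or when a new cancer treatment begins. A subject who starts new therapy before documented progression is no longer scanned, and so meets the final-analysis condition only by death or by leaving the study. Rerunning step 3 (post-progression median 6) with an assumed 5% or 10% of such subjects, each meeting the condition only at death:

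| PFS median (months) | 0% | 5% | 10% |
|---|---|---|---|
| 2 | 22 | 12 | 7 |
| 3 | 13 | 8 | 5 |
| 4 | 8 | 5 | 3 |

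With a post-progression median of 12 months and PFS 2, a 5% share takes 33 down to 9. Study withdrawals or moves to an extension protocol could shift the trigger the other way, so the size is not settled.

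**5. What a cohort loses.** A cohort's median survival can normally be estimated once 8 of 15 have died. With a post-progression median of 6 months and no adjustment for new therapy, 95%, 99% and 99.9% of cohorts have reached that point at the trigger for PFS medians 2, 3 and 4. The weak spot is long post-progression survival: at PFS 2 with a post-progression median of 12 months, the share is 55%.

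**6. What a complete estimate would be worth.** With all 15 deaths observed, an exponential median has a 95% interval of exp(±1.96/√15), or 0.60 to 1.66 times the estimate, and there is no control group.

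**7. Timing of the decision.** The review of a low-response cohort follows the ORR result, which is due after the opportunity for 4 cycles, or 4 × 3 = 12 weeks of treatment. The documents do not tie that review to month 36, so a survival cut at that date might come too late to inform it.

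**The case for a change.** The strongest argument for a change is that subjects are being contacted expressly for survival and the plan should say what becomes of the answer. In an uncontrolled trial with six cohorts, an open list of clinical-benefit parameters lets survival be called on where it flatters and passed over where it does not. Naming it, with a cut date, would cost a sentence, one data cut and one table per cohort, with no new data collection.

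Part of this stands. The synopsis is silent, its list is open, and the final-analysis condition does not wait for the follow-up to end. The rest carries less weight. The low-response review is a judgement over several measures with no threshold on any of them, so naming one more would not bind it. The exploratory objectives relate PK and biomarkers to clinical outcomes in open terms that can include survival. The synopsis also lists only primary and secondary endpoints and refers to Sections 1.3, 10 and 10.2 for the rest, so it cannot show that an exploratory survival summary is absent from the protocol.

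**Conclusion.** No change is called for. This is missing detail in a synopsis, and it does not make any result wrong. Followed as written, the plan gives sound ORR estimates, a sound 3-of-15 criterion, and unaffected PFS and safety summaries. Collection continues to 36 months whatever the date of the final analysis, and nothing bars a later cut. An analyst holding these data would summarise survival descriptively by cohort.

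The amount at issue runs from about 2 to 22 deaths of 90 for PFS medians of 6 down to 2 months, with a post-progression median of 6 months, and up to 33 if that median is 12. It is about 7 with unequal cohort medians, and roughly halves at the shortest PFS median if 5% of subjects start new therapy before documented progression. These figures rest on assumed exponential times, 12-month accrual and no other terminations, none of which the documents supply. The conclusion is limited to the synopsis, since the full objectives and statistical sections were not available.

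### Does using 90 for both enrolled and response-evaluable Part 2 subjects leave cohorts short of 15 or inflate the response rate?

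*Combined protocol and SAP*

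**What the plan says.** The Part 2 sample-size sentence in the Synopsis (Statistical Considerations) is "Approximately 90 subjects (15 response-evaluable subjects per cohort [tumor type]) will be enrolled in Part 2". The Synopsis Sample Size line gives the same figure as an evaluable count, "Part 2: approximately 90 response-evaluable subjects", and adds it to Part 1 for the study total: "Sample Size: Approximately 99 to 108 (Part 1: approximately 9 to 18 DLT-evaluable subjects". There are six cohorts; Study Design says "Enrollment into the 6 cohorts will occur in parallel, independent of one another".

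The decision rule appears with two denominators. Study Hypotheses has "at least 3 objective responses out of 15 evaluable subjects in at least 1 cohort". Statistical Considerations has "at least 3 out of 15 subjects have an objective response (an ORR of at least 20" (a percentage), without the word evaluable. The primary estimate is described there as a proportion of subjects, with an exact 95% interval for each cohort, and no analysis set is named.

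Key Inclusion Criteria require "Measurable disease (at least one measurable lesion) (Part 2" only). The Sample Size line refers to Sections 3.3 and 10.3 for detail, and Statistical Considerations refers to Section 10. Only the Synopsis was available for this check.

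**The concern.** If some enrolled subjects are not evaluable, 90 enrolled cannot yield 90 evaluable. Measurable disease is already an entry criterion, so response-evaluable seems to refer to something that happens after entry, such as being dosed or having a follow-up scan. The first scan is due at 6 weeks. In advanced disease, the subjects who miss it will often have died, progressed clinically or stopped for toxicity, and none of them can be a confirmed responder.

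Two outcomes then suggest themselves. Without replacement, a cohort has fewer than 15 evaluable subjects and a rule written for 15 no longer fits. With replacement up to 15, enrolment exceeds 90 and early failures leave the denominator, so the primary endpoint is biased towards passing. In a cohort of 15, one response is worth 1/15 = 6.7 percentage points, so who is counted could decide whether a tumour type meets the criterion.

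**Working it through.** **Inputs.** From the Synopsis: 6 cohorts, 15 per cohort, a bar of 3 responses, and 9 to 18 subjects in Part 1. The non-evaluable share d is not given there. It is assumed here to be 10%, with a range of 5% to 20%.

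**1. The plan's own figures.** 6 × 15 = 90; 9 + 90 = 99; 18 + 90 = 108; 3/15 = 20%. All reproduce exactly, and none contains an allowance for losses. The Sample Size line labels Part 1 as DLT-evaluable and Part 2 as response-evaluable. The 99 to 108 is therefore a sum of evaluable counts, given as approximate.

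**2. The rule with 15 counted subjects.** P(X ≥ 3) = 1 − Σ(k = 0 to 2) C(15,k) p^k (1 − p)^(15 − k). This gives 3.6% at p = 5%, 18.4% at 10%, 60.2% at 20% and 87.3% at 30%.

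**3. First reading: 15 enrolled, no replacement.** The chance that all 15 are evaluable is (1 − d)^15:
- 0.95^15 = 46%
- 0.90^15 = 21%
- 0.80^15 = 3.5%

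Fewer than 15 evaluable is therefore likely on this reading, but that does not lower the chance of passing. If the unscanned subjects are all non-responders, the number of responders among the 15 enrolled is still binomial(15, p), where p is the all-treated ORR. P(X ≥ 3) at p = 20% stays at 60.2%. A fall to 49.8% appears only if the ORR is set at 20% among 13 evaluable subjects. That corresponds to 0.20 × 13/15 = 17.3% of all 15, which is a less active treatment and not a loss of power.

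**4. Second reading: unscanned subjects replaced until 15 are evaluable.** If all of them are non-responders, the ORR among evaluable subjects is q = p/(1 − d). For an all-treated ORR of 10%:

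| d | q | P(at least 3 of 15) | Expected Part 2 enrolment, 90/(1 − d), rounded up |
|---|---|---|---|
| 0 | 10.0% | 18.4% | 90 |
| 5% | 10.5% | 20.5% | 95 |
| 10% | 11.1% | 22.8% | 100 |
| 20% | 12.5% | 28.7% | 113 |

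For an all-treated ORR of 15% and d = 20%, q = 18.75% and the chance of passing goes from 39.6% to 55.4%.

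**5. Third reading: evaluable means treated, with measurable disease at baseline, and unscanned subjects count as non-responders.** Every Part 2 subject has measurable disease by the entry criterion, so only undosed subjects drop out. In essence all 15 count, 90 enrolled gives about 90 analysed, and the chances in step 2 apply unchanged.

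**6. Scale.** The exact 95% interval for 3/15 is 4.3% to 48.1%. At an all-treated ORR of 10%, the shift under the second reading is 11.1 − 10.0 = 1.1 points at d = 10% and 12.5 − 10.0 = 2.5 points at d = 20%.

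**The case for a change.** The best case for acting is that the wording really is inconsistent. One number serves two populations, and the 3-in-15 rule is stated once on evaluable subjects and once on subjects. The third reading is nowhere spelled out in the Synopsis, and the word approximately does not say who is in the denominator. If evaluable did mean having a follow-up scan, with replacement, the bias would run one way, towards passing. The wider review of benefit and safety would not catch it, because the Synopsis calls for that review only when 2 or fewer subjects respond. Stating the denominator would cost a sentence.

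The inconsistency and the direction of the conditional bias both stand. What does not stand is the step from an undefined term to a wrong result. The Synopsis does not say that unscanned subjects are removed or replaced, and it describes the primary estimate as a proportion of subjects. The sections that would hold the definition and any replacement rule are cited but were not available, so they cannot be called absent. The loss rate has no source in the text, and entry requires ECOG 0 or 1 and at least 3 months' life expectancy, which favours reaching a 6-week scan. The remedy one would propose, all treated subjects with baseline measurable disease, is one natural meaning of the existing term.

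**Conclusion.** No change follows. The arithmetic is internally consistent, and the claim that cohorts must either fall short or overstate the ORR fails because a third, ordinary reading gives neither result. What remains is a gap in definition around an approximate figure. An analyst would fill it sensibly by counting all treated subjects with measurable disease at baseline and treating those without a follow-up scan as non-responders.

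This conclusion assumes that Sections 3.3 and 10.3 do not exclude or replace unscanned subjects. If they do, step 4 gives the size: the ORR is multiplied by 1/(1 − d), which is 1.05 to 1.25 for d of 5% to 20%, and enrolment would exceed 90. Even then the effect is modest for an uncontrolled study that estimates ORR in cohorts of 15, for which the Synopsis states no error rate or power. A cohort that misses the bar is reviewed on other evidence and not dropped automatically.
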